- 4) The BrainPort already has CE Mark approval and pending FDA approval (final safety study documents submitted to the FDA August 2013), and should be available for purchase by 2014, at least in Europe and Canada. Whether the device could be useful in a pediatric population is an important clinical question.
- 5) The relation of the anticipated benefit to the risk presented by the study is at least as favorable to the subjects as that provided by available alternative approaches (blind training).

RESEARCH DESIGN AND METHODS

Primary Efficacy Endpoints

The primary efficacy endpoint for this study is a statistical analysis of subjects' improvement over baseline in any of the following areas: light detection, light localization, movement perception, and standardized object recognition tasks after use of the BrainPort. To test our primary endpoints, we will use a within-subjects repeated measures design.

Statistical analysis (general)

All data will be stored in a password encrypted PASS Statistics version 18 database whose contents will be available only to members of the study team. We will use t-tests to assess the differences in performance for all measures on our assessment battery, pre- and post-training. Bonferoni correction will be used to correct for experiment-wise error rate (*i.e.*, the increased possibility of finding many significant correlations due to the multiple tests conducted). Separate analyses of covariance will be performed using age, sex, education, and years since diagnosis as covariates. The major advantage of this design is subject homogeneity; that is, random subject effects are reduced. Because the subjects serve as their own controls, factors such as age, education, mental status, motivation, and disease are completely matched; thus these factors will not contribute to the main effect of training. Matching is always very difficult in individuals with eye disease, and this design resolves this confound.

Subject selection criteria

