Following consent, subjects will complete baseline psychophysical assessments which have been used in similar BrainPort studies. These consist of simple and easy to understand computer based tests of the ability to detect light, direction, motion, and letters. In addition, we may administer seated tests where the subject is asked to recognize objects, pictures or depth cues. Each of these tests takes between 5 and 15 minutes to complete.

Following baseline studies, a structured "Clinical Training Phase" with the will occur. Our lab has trained over 100 subjects to use the BrainPort device (largest center worldwide), and has established the methods to provide core skill acquisition under the direction of an occupational therapist who works in our laboratory (refer to attachment). Because the subjects in this study will not be taking the device home, but will be restricted to limited use in the controlled laboratory setting, the training will not have to involve outdoor navigation or more advanced skills. After the Brainport training phase has been completed, and the subject has demonstrated basic proficiency with the device, the same set of outcomes assessments administered at baseline will be repeated.

If at any point during the study, the subject subsequently does not meet inclusion criteria or satisfies exclusion criteria, or wishes to stop participation, further testing will be discontinued and the subject will be dismissed.

Detailed description of study design by visit:

Session 1:

- Informed consent
- Review of inclusion and exclusion criteria
- Baseline medical and medication history
- Oral exam
- Baseline psychophysical assessments

Session 2, 3, & 4:

- Training session
- Oral exam

Session 5:

- Repeat outcomes assessments with Brainport
- Oral exam

Each session is expected to last 90 minutes, will be performed at the UPMC, and will be performed by the Research Staff and/or PI.

Note: follow up visits can be combined into a single longer day with morning and afternoon sessions at the request of the subject. We are allowing this because subjects and their families are responsible for their own travel, lodging and meal expenses.

Evaluation Procedures/Outcomes Assessments (Detailed descriptions):

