Potential subjects will be examined to verify that vision in each eye is light perception or worse by the PI according to standard practices at the UPMC Eye Center. Subjects will not need to be dilated. In most cases, our blind subjects have prosthetic eyes or have such badly damaged eyes that verification of blindness by clinical exam does not need to occur. In these instances, the ocular examination will be waived. Inspection of the oral cavity, medical and medication history will be performed.

Psychophysical assessments: We begin with rudimentary vision assessment such as light perception and proceed to increasingly complex visual tasks which approach "normal" vision as the device allows. In the event that a subject is not able to perceive better than light perception, tests which ascertain higher functions will not be administered. Below is a representative description of the tests that we commonly employ with BrainPort studies.

The Basic Assessment of Light Motion (BaLM) and Basic Assessment of Grating Acuity (BaGA) have been developed with the intent of testing artificial vision devices, which provide the most rudimentary visual precepts. They have been used to quantify such qualities as light detection, temporal resolution and light motion as well as "grating acuity" for situations where standard resolution acuity is nonexistent. The methods for testing have been described in Artificial Vision by Mark Humayan. Both tests run on a software platform and are presented on a computer LCD screen to the subject. The stimuli they present consist mainly of large targets of varying patterns. The subject is seated in a regular chair while looking at a computer display for these non-invasive tests, each of which last an average of 10 minutes or less. The subject is able to stop the test in the event they feel they need to get up and move around. All visual acuity measurements will be performed by a single examiner. For baseline testing, while one eye is tested, the other will be occluded. We use this to make sure that both eyes have visual acuity of LP or worse to meet entry criteria. Subsequent testing using the Brainport is done using the camera pointed at the computer screen. All vision tests will be performed in a room with standardized illumination.

BaLM Test

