This test consists of a battery of four modules for perception of light, time, location, and motion. For this study, we will only use the light and location modules. In a preferences screen, the variables of the tests can be determined and the test can be calibrated to projecting distance and image size.

Upon starting the first subtest the program runs self-paced, requiring the patient to enter an alternative choice response via a numeric keypad. Most visually impaired subjects are familiar with a numeric keypad. At the beginning of each test there is a short sound to prompt a patient's response. After the patient has pressed the corresponding key, two different sounds are played to indicate either a right or a wrong response.

Light Detection

After the initial sound a full-field flash appears, or the display stays black in a random fashion (maximal screen luminance in our setup is 5100 cd/m^2 , Michelson contrast of 99.5%). The patient has to indicate whether he has seen a flash or not. The duration of the flashes can be adjusted in the preferences screen. Hit rates at different brightness as well as the stimulation parameters are recorded.

Light Localization

A fixation target appears in the middle of the display, followed after a few seconds by a wedge-shaped bright field with its tip on the central fixation dot. The base is oriented in one of eight directions (up, down, left, right, and four obliques). The patient is asked to enter the direction, and then a randomly chosen new direction is presented. The number of possible directions can also be limited to four (up, down, left, and right).

BaGA Test

This test is similar to the BaLM test described above, but the presented stimulus consists of sine wave gratings of increasing or decreasing frequency. Grating acuity is often used in vision research to determine level of visual function. In a preferences screen, the variables of the four tests can be determined and the test can be calibrated to projecting distance and image size.

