Upon starting the first subtest the program runs self-paced, requiring the patient to enter an alternative choice response via a numeric keypad. Most visually impaired subjects are familiar with a numeric keypad. At the beginning of each test there is a short sound to prompt a patient's response. After the patient has pressed the corresponding key, two different sounds are played to indicate either a right or a wrong response. Hit rates and stimulation patterns (frequency of sine wave grating, orientation and contrast) are recorded.

Analysis of Test Results

The BaLM and BaGA tests automatically calculate percentages of correct responses of each test, as well as mean reaction times and standard deviation of measurements for each test. ANOVA analyses will be completed to compare pre- Brainport and post- Brainport use. Analysis will also be completed to compare performance between those with acquired versus congenital blindness, age, gender and presence of TBI.

Object Recognition Tasks

Object recognition tasks which involve the subject seated at a desk will be undertaken. These tests will involve tasks that will first ask the subject whether an object is present or not (2 choice discrimination). If successful, then the more complex discrimination tasks will be employed, which will ask the subject to recognize a specific object out of a choice of 3 objects or 5 objects. Testing will be repeated for 20 trials each.

Analysis of Test Results

All data is recorded into a password protected PASW database. Primary performances measure the ability to detect whether an object is or is not present, as well as to recognize a specific object within a field of other objects. Secondary measures include time to object recognition. ANOVA analysis will be completed to compare pre-Brainpor and post-Brainport use. Additional analysis will compare performance between those with congenital versus acquired blindness, age, gender and presence of TBI.

ADVERSE EVENTS

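### Movement perception is a primary efficacy area, but the BaLM section excludes the only motion test the protocol names

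*Combined protocol and SAP*

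**What the plan says.** Primary Efficacy Endpoints counts improvement over baseline in at least one of four areas: "light detection, light localization, movement perception, and standardized object recognition tasks after use of the BrainPort". Statistical analysis (general) adds: "We will use t-tests to assess the differences in performance for all measures on our assessment battery, pre- and post-training". A Bonferroni correction applies, but its divisor is not given.

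Overview of Study Design describes the baseline assessments as "computer based tests of the ability to detect light, direction, motion, and letters" and says that after training "the same set of outcomes assessments administered at baseline will be repeated".

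The BaLM Test section says: "This test consists of a battery of four modules for perception of light, time, location, and motion". It continues: "For this study, we will only use the light and location modules". Only light detection and light localization are then set out in detail.

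For BaGA, the stimulus is a sine wave grating, and "Hit rates and stimulation patterns (frequency of sine wave grating, orientation and contrast) are recorded". Object Recognition Tasks and the analysis text after it score presence, identity and time to recognition.

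Two further statements under Evaluation Procedures/Outcomes Assessments bear on the point. The test list is introduced with "Below is a representative description of the tests that we commonly employ with BrainPort studies". The same paragraph says that a subject who cannot perceive more than light will not be given tests of higher functions.

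**The concern.** The endpoint section and the overview agree that movement is to be measured before and after training. The BaLM section, in a sentence specific to this study, drops the module that would measure it. Staff who follow the BaLM section collect nothing on movement; staff who follow the overview need a motion test that the protocol does not specify.

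The loss would be permanent for each subject affected. The design compares each child with his or her own untrained baseline, and training starts at Session 2, so a motion baseline missed at Session 1 cannot be obtained later.

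There is also a smaller problem of definition. When success means improvement in at least one of several areas, the list of areas tested is part of the success rule. If it is open whether movement is tested, the number of chances to succeed and the Bonferroni divisor are open too.

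**Working it through.** This is mainly a comparison of texts. The arithmetic at the end is context.

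**1. Which primary areas have a named test in use?**

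| Primary area | Test in use | Section |
|---|---|---|
| Light detection | BaLM light module | BaLM Test |
| Light localization | BaLM location module | BaLM Test |
| Object recognition | Presence task, then 3- and 5-object tasks | Object Recognition Tasks |
| Movement perception | None; BaLM motion module excluded | BaLM Test |

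Three of four areas are covered; 1/4 = 25% are not.

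**2. Could another test supply a motion score?** BaGA records grating frequency, orientation and contrast; no moving stimulus or motion response is described. The object tasks record presence, identity and time. The training curriculum contains no motion outcome test.

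**3. How many movement scores are at issue?** With 8 subjects (Subject selection criteria) assessed at Sessions 1 and 5, the maximum is 8 × 2 = 16, and fewer if a subject stops or a test is withheld. If the BaLM section is followed and nothing else is run, the number is 0.

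**4. Would adding the module be enough?** Not necessarily. Inclusion criterion 2 requires light perception or worse in both eyes. At the no-device baseline, every eligible subject therefore falls under the rule that withholds higher-function tests. The protocol does not say whether motion is such a function. If it is, the module could be added to Session 1 and still yield no baseline scores.

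**5. Context: the Bonferroni family.** The plan's own figure (8 subjects, p<0.05, power above 0.8) cannot be reproduced, because no effect size or SD is given. For a paired t-test with n = 8 and df = 7, let d = mean change / SD of change, with noncentrality d√8. Unadjusted two-sided 0.05 gives 80% power at d = 1.16. Assuming one two-sided test per area:

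| Tests counted | Alpha | Critical t | d for 80% power |
|---|---|---|---|
| 3 (no movement) | 0.05/3 = 0.0167 | 3.128 | 1.45 |
| 4 (with movement) | 0.05/4 = 0.0125 | 3.335 | 1.53 |

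Counting movement in the divisor without running it lowers power at d = 1.45 from 0.80 to 0.75.

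If the family is instead the described percent-correct measures (BaLM light, BaLM location, BaGA and three object tasks, with or without BaLM motion), the divisors are 6 and 7. The alphas are then 0.0083 and 0.0071, and d is 1.65 and 1.70.

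**The case against.** The best reply is that the test list is introduced as representative, so a motion test may be run without being listed. The overview mentions a letters test that has no description in the assessment section either, so a missing description does not prove a missing test. The motion module itself is only named, never described. This stands as far as it goes: a reader might infer that no movement data are or will be collected, and the documents do not establish that. It does not remove the conflict. The BaLM restriction is written for this study, and a primary area needs a stated measure.

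A second reply is that success needs improvement in only one area. That also stands. A reader might infer that the primary endpoint cannot be analysed; it can, through light detection, light localization and object recognition.

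A third reply is that the Bonferroni family is undefined whether or not motion is tested. This is correct. Statistical analysis (general) speaks of all measures in the battery. Even the count of 6 or 7 omits reaction times, time to recognition, letters, pictures and depth cues. The detectable-effect figures therefore should not be read as the harm done by this contradiction.

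**Conclusion.** The contradiction is explicit and needs correction. Primary Efficacy Endpoints and Overview of Study Design call for a movement measure before and after training; the BaLM Test section excludes the only named one, and no other described test replaces it. If that section is followed and no unnamed motion test is run, one of four declared primary areas has no data.

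The main loss is the movement question itself. The effect on the other three areas is small: 1.45 against 1.53 SD at n = 8 for three against four tests. That comparison is illustrative and assumes two-sided tests and one test per area, neither of which the protocol states.

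The documents do not show how many subjects have completed Session 1 or what was administered, so the remedy depends on facts outside them.

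**What to change.** Reconcile four places before any outcome analysis: Primary Efficacy Endpoints, Overview of Study Design, the psychophysical assessments paragraph and BaLM Test. The route depends on what has been done.

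- **No subject has completed Session 1.** Change BaLM Test to use the light, location and motion modules at Sessions 1 and 5, with percent correct as the movement score (BaLM already calculates it). State whether the rule withholding higher-function tests applies to motion at the no-device baseline, so that baseline scores will exist.
- **A motion test was given at Session 1 to all subjects so far.** Name it, correct BaLM Test to match, and give the same test at Session 1 to any remaining subjects and at Session 5 to all.
- **Motion was not tested at Session 1 for some or all subjects.** Take movement perception out of the primary analysis by a dated amendment. Report it as planned but not, or incompletely, assessed, and treat any motion data as exploratory.

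In every case, list by name the tests in the Bonferroni family and count only those actually run.

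Cost: the first route adds one short computer test at each of two sessions. At the overview's 5 to 15 minutes per test, that is 2 × 5 to 2 × 15 = 10 to 30 minutes per subject, to be checked against the 90-minute session limit. It is less if the average of 10 minutes or less given under psychophysical assessments covers the whole of BaLM. The second route continues a test already in use and changes wording; the third changes wording and reporting only.

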We will recruit 8 blind subjects between the ages of 7 and 18 from the UPMC Eye Center patient population, the Wicab website, the established volunteer list of over 200 blind subjects from the Sensory Substitution Laboratory, the Clinical Trials Registry at the University of Pittsburgh and the patient population at the ophthalmology department at the UPMC Children's Hospital. Recruitment of normally sighted controls is not justified. We expect to screen 15 blind subjects to achieve our enrollment target. Based upon estimates from our preliminary data, this sample size should allow us to show differences between the naïve and BrainPort condition with a significance level of p<0.05 and a power of greater than 0.8.

We will attempt to enroll an equal number of males and females to the extent this is possible. We will attempt to enroll minority populations in our study.

Inclusion Criteria

Volunteer subjects enrolled and treated in this study must meet all of the following criteria:

- 1. Between the age of 7 and 18
- 2. Blind (documented visual acuity of light perception or worse) in both eyes from an eye care provider.
- 3. Able to read (or have read to him or her), understand and sign the Informed Consent and Assent form.
- 4. Able to understand the training and rehabilitation protocols involved in the study.
- 5. Willing to use the BrainPort device

Exclusion Criteria

Subjects will be excluded from the study if they meet any of the following criteria:

- 1. Current oral health problems as determined by the subject's history, and an examination of the oral cavity performed by a member of the study team. Subject is excluded if any of the following conditions are met:
 - a. A history of injury to the tongue resulting in impaired sensation or use of the tongue.
 - b. Visible open lesions, cold sores, abrasions, blisters, or rash on the tongue.
 - c. Oral surgery or dental work in the past 3 months or anticipated to occur for the duration of participation in the study (does not include routine dental health exams/cleanings).
 - d. Piercing on the tongue.
 - e. Performance better than 20/5000 on the FrACT acuity test (same visual criteria as FDA safety study).
- 2. Known neuropathies of tongue or skin tactile system.
- 3. Unwilling or unable to adhere to all study requirements, including completion of the training period, evaluation tests and follow up visits.
- 4. Implanted electrical medical devices such as pacemakers.

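### Replacing Bonferroni with Holm's step-down procedure keeps the same experiment-wise error control and gives 8 subjects more power to show which areas improved

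*Combined protocol and SAP*

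**What the plan says.** Under Primary Efficacy Endpoints, success is "improvement over baseline in any of the following areas: light detection, light localization, movement perception, and standardized object recognition tasks". Under Statistical analysis (general), the test is fixed: "We will use t-tests to assess the differences in performance for all measures on our assessment battery, pre- and post-training". The multiplicity method follows: "Bonferoni correction will be used to correct for experiment-wise error rate". The number of tests in the correction and the resulting per-test level are not given.

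The sample-size statement under Subject selection criteria plans 8 subjects and cites unreported preliminary data for a difference between the naive and BrainPort conditions "with a significance level of p<0.05 and a power of greater than 0.8". It gives no effect size, SD of change, sidedness or powered measure. It does not say whether 0.05 is per test or experiment-wise.

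The later Analysis of Test Results sections call the pre/post comparison an ANOVA. With two time points within subject, that is the same test as the paired t-test (F = t²).

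**The concern.** With 8 subjects and several measures, the choice of multiplicity correction matters. Bonferroni holds every test to 0.05/k (k = number of tests), even after other areas have already been declared improved. Holm relaxes the threshold as areas are declared, with no loss of error control. If the device helps in several areas, Bonferroni will more often leave real improvements undeclared. Which functions improve in blind children is much of what this study can teach, so that loss is worth avoiding when avoiding it costs so little.

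A secondary matter is that the only power figure in the plan is not linked to the corrected level at which the tests will be judged.

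**Working it through.** **Inputs from the protocol.** n = 8, each subject as own control; paired t-tests; Bonferroni; power above 0.8 at p<0.05.

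**Assumptions.** Two-sided tests. k = 4, one test for each area named in the primary endpoint. The text does not fix k: movement perception is a named area, yet the BaLM Test section says "For this study, we will only use the light and location modules", while tests on all measures could mean more than four. All 8 subjects have every measure. Some tests are conditional ("If successful, then the more complex discrimination tasks will be employed"), but no rate is given, so no smaller n is modelled. Paired differences are normal and equally correlated between areas.

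**Step 1. The plan's own figure.** Power of a paired t-test is P(|T| > t_crit), where T is noncentral t with n − 1 = 7 df and noncentrality dz × √n, and dz = mean/SD of paired change. Without dz, the figure above 0.8 cannot be reproduced. Solving backwards at 0.05 (t_crit = 2.365), power of 0.80 needs dz = 1.156 (noncentrality 1.156 × √8 = 3.270), and power of 0.90 needs dz = 1.342.

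**Step 2. The same effects at the Bonferroni level.** 0.05/4 = 0.0125 (t_crit = 3.335). Per-test power is 0.52 at dz = 1.156 and 0.67 at dz = 1.342. For 0.80 per test with n = 8, dz must be 1.45 (three tests), 1.53 (four) or 1.60 (five).

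**Step 3. Holm.** Order the p-values and compare the j-th smallest with 0.05/(k − j + 1), stopping at the first failure. For k = 4 the thresholds are 0.0125, 0.0167, 0.025 and 0.05.
- *Error control.* If k0 null hypotheses are true, the first true null is reached at step k − k0 + 1 at the latest, so its threshold is at most 0.05/k0. The chance of any false rejection is then at most k0 × 0.05/k0 = 0.05, whatever the correlation.
- *Power.* No threshold is below 0.05/k, so Holm rejects everything Bonferroni rejects.
- *At least one significant area.* The first step is the same as Bonferroni's, so this event is the same under both methods.

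**Step 4. Size of the gain.** Simulation, 200,000 runs, average power per responding area:

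| dz | Areas responding (of 4) | Bonferroni | Holm, correlation 0 / 0.5 / 0.9 |
|---|---|---|---|
| 1.156 | 4 | 0.52 | 0.67 / 0.65 / 0.62 |
| 1.156 | 3 | 0.52 | 0.60 / 0.59 / 0.58 |
| 1.156 | 2 | 0.52 | about 0.55 throughout |
| 1.156 | 1 | 0.52 | 0.52-0.53 |
| 1.342 | 4 | 0.67 | 0.84 / 0.81 / 0.76 |

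**Step 5. Power for any area.** With four areas responding and correlations 0 / 0.5 / 0.9, the chance of at least one significant area is about 0.95 / 0.85 / 0.67 at dz = 1.156 and 0.99 / 0.94 / 0.80 at dz = 1.342, identical under both methods. When fewer areas respond, Holm raises the chance of detecting at least one of them by at most about 0.003.

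**The case against.** Bonferroni is a valid method, and nothing in the plan is wrong for using it. Success in any one area is enough, and Holm does not help that claim when all areas respond. Both objections stand. With a single responding area the gain is negligible. Bonferroni also comes with simple simultaneous confidence intervals, an advantage that Holm partly gives up. What remains is that Holm gives the same protection, never declares fewer areas, and declares more of them when two or more respond.

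A reader might go further and infer that the sample-size claim is false because power drops to 0.52 after correction. The documents do not support that, for four reasons:
- The claim is a lower bound with no effect size, and 0.52 belongs only to the smallest effect that satisfies it. At dz of 1.53 or more, per-test power at 0.0125 is still at least 0.80.
- The 0.05 may already be the experiment-wise level.
- Success is defined over any area. With all four responding, that power stays above 0.8 up to a correlation of about 0.65 even at dz = 1.156, and is about 0.80 at a correlation of 0.9 when dz = 1.342.
- The number of tests is assumed.

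Power can fall short when few areas respond or the areas are highly correlated, but nothing in the documents says that either is the case.

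**Conclusion.** This is a free improvement, not the correction of an error. Holm over the same tests keeps experiment-wise control and is at least as powerful as Bonferroni for any number of tests, effect or correlation. The size of the gain is illustrative. With four tests and all areas responding, average power per area rises by 0.10 to 0.15 at dz = 1.156 (0.52 to 0.62-0.67) and by 0.09 to 0.17 at dz = 1.342 (0.67 to 0.76-0.84). It is smaller with fewer responding areas. These figures rest on two-sided paired t-tests, complete data on 8 subjects and equally correlated normal differences. The benefit is in naming the areas that improved, not in the chance that the study succeeds in at least one.

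The missing link between the stated power and the corrected level is a secondary reporting gap. Power is unsupported at that level, but it is not shown to be below 0.8.

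**What to change.** In Statistical analysis (general), replace the Bonferroni sentence with, for example: *P-values from the pre/post comparisons will be adjusted by the Holm step-down procedure, applied to the same set of tests, to control the experiment-wise error rate at 0.05.* The team should confirm 0.05 as the experiment-wise level, since the plan does not state it.

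Cost: one sentence and no added subjects, visits or measurements. The small downside is that simultaneous confidence intervals matching Holm are less simple. Bonferroni intervals can still be reported beside the Holm decisions, but may occasionally include zero for an area that Holm declares improved.

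When the sample-size statement is next edited, say whether p<0.05 is experiment-wise and whether power is per area or for any area, and give the detectable effect. For four tests at 0.0125 and 8 subjects, 80% power per area needs a mean/SD of paired change of about 1.53 (1.45 for three tests, 1.60 for five). These values are for Bonferroni and are therefore conservative under Holm. This edit is also wording only.
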